5.1.2. Secondary outcomes

1. Access-related complications per patient-year

Separate analyses will be performed on access-related complications graded as Clavien-Dindo grade 2 or higher and on access-related complications graded as Clavien-Dindo grade 4 or 5. The outcome will be defined as the number of access-related complications per patient-year.

- Access-related complications of Clavien-Dindo grade 2 or higher will be registered (30). Grade 2 complications require pharmacological treatment including catheter thrombolysis, antibiotics and blood transfusions. Complications that require no pharmaceutical or interventional treatment (grade 1) are not considered relevant for this clinical trial.
- Access-related complication of Clavien-Dindo grade 4 or 5 (i.e. admission to intensive care unit or death) are considered serious adverse events. As an exception, postoperative intensive care unit admission for vasopressor therapy to prevent early vascular access thrombosis is not considered a serious adverse event or complication.

2. Vascular access thrombosis rate

Vascular access thromboses will be defined as the absence of thrill and bruit, with confirmation of no flow by duplex ultrasound if deemed necessary by the treating physician at the study site. The outcome will be defined as the number of vascular access thrombosis events per person-year.

3. All-cause mortality

All-cause mortality will be defined as death by any cause during follow-up.

4. Access-related health care costs from randomization until the end of follow-up

Healthcare costs will be derived from hospital registration systems at the individual participant level. Costs to patients and families will be measured at the individual participants level using a study-specific adaptation of the Medical Consumption Questionnaire and Productivity Cost Questionnaire

developed by the institute for Medical Technology Assessment. Patients will be asked to report the data from their cost questionnaire every 3 months during the follow-up period.

5. Patient-reported outcome measures

For the patient-reported outcome measures the Short-form Vascular Access Questionnaire (SF-VAQ) and the Dutch version of the 5-level EuroQol 5-dimensional questionnaire (EQ-5D-5L) will be used.

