5.2.2. Secondary outcomes

Serious adverse events, access-related complications and vascular access thrombosis:

The number of access-related complications and access-related thromboses for each patient-year of haemodialysis treatment will be analysed using a general linear mixed effect model with Poisson distribution and identity link, and with time as off-set variable. The outcome will be expressed as a ratio (exponential of β_1) of events (number of interventions) per 1 unit increase of exposure time between both groups. A random intercept for each individual participant will be estimated to account for dependence of observations. Expected counts will be plotted against observed counts to check whether the distribution of counts follow a Poisson distribution. Furthermore, the Pearson dispersion statistic will be assessed to check whether there is equidispersion of the variance compared to the mean. In case of overdispersion of the data, a quasi-Poisson model or negative binomial model will be performed. Sensitivity analyses will be done for the primary outcome with major interventions having twice the weight of minor interventions, and with exclusion of patients with access-related interventions with technical failure (residual stenosis $>30\%$) and clinical failure (flow volume $<500\text{mL/min}$ in the first week after intervention and/or failure to restore vascular access function and clinical signs of flow dysfunction).

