Stratification for study site and vascular access type (fistula / graft).

Subgroup analysis: vascular access type (fistula / graft).

Sensitivity analysis:

- Exclusion of patients with interventions with technical failure (see Table 7A)
- Exclusion of patients with interventions with clinical failure (see Table 7A)

Table 4B: Access-related adverse events

	Monitoring (... patient-years)	Surveillance (...patient-years)	Event rate ratio (95% CI)	P
Access-related adverse events	N	N	... (....)	...
Pain requiring medication (days)	N	N	... (....)	...
Infection requiring antibiotics (days)	N	N	... (....)	...
Bleeding requiring blood transfusion	N	N	... (....)	...
Central venous catheter thrombolysis	N	N	... (....)	...

Statistical analysis (intention to treat population): general linear mixed effect model with Poisson distribution and identity link, and with time as off-set variable (see Table 3A for details).

Table 4C: Hospital admittance

	Monitoring (...patient-years)	Surveillance (...patient-years)	Event rate ratio (95% CI)	P
Hospital admittance (days)	N	N	... (...-...)	...
Related to vascular access	N	N	... (...-...)	...
Unrelated to vascular access	N	N	... (...-...)	...

Statistical analysis (intention to treat population): general linear mixed effect model with Poisson distribution and identity link, and with time as off-set variable (see Table 3A for details).

Table 4D: Line listing of serious adverse events

Table 4E: Line listing of protocol deviations

Table 5A: SF-VAQ scores at baseline

	All patients (N=...)	Monitoring (N=...)	Surveillance (N=...)	P
Total score
Physical domain
Pain
Bleeding
Swelling
Bruising
Social functioning domain
Daily activities
Appearance
Sleep
Bathing and showering
Dialysis complications domain
Problem on dialysis
Access care
Hospitalization
Worry about access longevity

Groups are based on initial randomization

Include only questionnaires with complete data. Questions are Likert scores from 1 to 7. Domain scores are the sum of the 4 questions. The total score is the sum of the 3 domains.

Statistical analysis: Students t-test.

Table 5B: SF-VAQ scores according to the number of interventions during follow-up

	No interventions during follow-up (N=...)	1 intervention during follow-up (N=...)	>1 intervention during follow-up (N=...)	P
Total score
Physical domain
Pain
Bleeding
Swelling
Bruising
Social functioning domain
Daily activities
Appearance
Sleep
Bathing and showering
Dialysis complications domain

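### Table 4B counts pain and infection in days of treatment and reports event rate ratios, while the secondary outcome is the number of access-related complications per patient-year

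*SAP*

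**What the plan says.** Section 5.1.2, item 1, of the SAP fixes the unit: "The outcome will be defined as the number of access-related complications per patient-year". It also says which complications enter at the lower end: "Grade 2 complications require pharmacological treatment including catheter thrombolysis, antibiotics and blood transfusions". Pain is not named there, but pain that needs medication falls under drug treatment as the sentence is worded.

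Section 5.2.2 keeps the same unit for the analysis: "The number of access-related complications and access-related thromboses for each patient-year of haemodialysis treatment" go into a Poisson mixed model with follow-up time as offset.

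Table 4B, in section 6, is the shell for these drug-treated complications. Under a heading row for access-related adverse events it lists four components:

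- "Pain requiring medication (days", that is, in days
- "Infection requiring antibiotics (days", also in days
- "Bleeding requiring blood transfusion", with no unit of time
- "Central venous catheter thrombolysis", with no unit of time

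Every row, including the heading row, shares the column "Event rate ratio (95% CI", a P value and the Poisson mixed model detailed under Table 3A.

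**The concern.** The outcome is a number of complications, yet two of the four components in its table are numbers of treatment days. A programmer who follows the shell would add up antibiotic days and analgesic days per arm, divide by patient-years, and label the quotient an event rate ratio. That quantity answers a different question from the one in section 5.1.2.

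This is the first-listed secondary outcome, and section 1.2 states the aim of finding out whether surveillance can safely be abandoned. A ratio driven by a few long courses in one arm could hide a difference in how often complications occur, or suggest one that is absent. The heading row adds a second problem: it sits above rows in two different units, and the SAP does not say how it is formed.

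**Working it through.** The SAP gives no figure for this outcome, so there is none to reproduce. The check sets the texts side by side and then illustrates the consequence.

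**1. Is the label really a day count?** Table 4C, directly below, uses the same label for hospital admittance, and section 5.1.2, item 7, does define that outcome in days per patient-year. So in this SAP the label means a count of days. No item of section 5.1.2 defines days of antibiotics or days of pain medication as an outcome.

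**2. Does another output give the count?** No.
- Table 2G gives infection as a share of monitoring reports.
- Table 3B gives infection as an indication for intervention.
- Table 3D gives procedural complications as percentages.
- Table 4A covers serious adverse events.
- Table 4C covers hospital days.

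None reports the number of antibiotic-treated infections, or of medicated pain episodes, per patient-year.

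**3. What does the day ratio measure?** With equal follow-up in both arms,

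day ratio = (episodes in A × mean days in A) / (episodes in B × mean days in B) = episode ratio × ratio of mean course lengths.

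The two ratios agree only if mean course length is the same in both arms. The counts and course lengths below are assumptions, because the SAP gives none.

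| Infections, A vs B | Mean course in days, A vs B | Episode ratio | Day ratio |
|---|---|---|---|
| 20 vs 20 | 14 vs 7 | 20/20 = 1.0 | 280/140 = 2.0 |
| 30 vs 20 | 7 vs 14 | 30/20 = 1.5 | 210/280 = 0.75 |

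In the first row a doubling appears where the number of infections is equal. In the second the direction reverses.

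**4. Precision.** Days within one course are not independent events. If episodes are Poisson and each contributes D days, the variance-to-mean ratio of total days is φ = E[D²]/E[D]. A Poisson test at nominal 0.05 that ignores this has type I error 2 × (1 − Φ(1.96/√φ)).
- Fixed courses of 5 to 14 days: φ = 5 to 14, error about 0.38 to 0.60.
- Geometric course lengths with the same means: φ = 9 to 27, error about 0.51 to 0.71.

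One case was simulated, with a geometric mean of 10 days, an assumed 0.1 infections per patient-year and 414 patient-years per arm. It gave 0.64, against 0.65 by formula. These figures are for an unadjusted test only. The SAP plans a random intercept and, under overdispersion, a quasi-Poisson or negative binomial model, which would reduce the error. They would not turn a ratio of days into a ratio of complications, so the point rests on step 3.

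**The case against.** The strongest reply is that sections 5.1.2 and 5.2.2 already fix the analysed outcome as a count, and section 5.5 sends the analysis of harms to 5.2.2. The heading row of Table 4B has no day label. It can be read as the number of events, with the two day rows as added measures of treatment burden. On that reading, one footnote would settle the matter.

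Much of this stands. A reader might infer that the heading row adds days to events, so that a 14-day antibiotic course counts 14 and a transfused bleed counts 1, and bleeding and thrombolysis are swamped in the total. The SAP does not say so, and its definitions point towards a count. Bleeding and thrombolysis also keep their own rows and ratios either way.

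Two further points of the reply are right:
- The ratio heading alone does not prove that days were mistaken for events. Table 4C applies the same heading and the same model to hospital days, which are a defined outcome.
- Table 4B could not equal the section 5.1.2 outcome even with episodes throughout. That outcome is grade 2 or higher. Section 5.1.1 links grades 3A and 3B to the interventions shown in Table 3A, and deaths are in Table 4A.

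The reply does not remove the mismatch in the pain and infection rows. Treatment days are nowhere defined as an outcome, and these rows are the only planned comparison of drug-treated infection and pain between the arms.

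**Conclusion.** The contradiction of units is in the current text and is certain for two of the four component rows. Followed as written, the pain and infection ratios depend on incidence and treatment length together. They depart from the ratio of complications by the factor by which mean course length differs between arms. In the assumed example, 1.5 becomes 0.75.

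The size in this trial is unknown, because the SAP gives no expected counts or durations. If mean course lengths turn out equal, the point estimates would agree.

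How the heading row is formed is an open definition, not a demonstrated error. The texts do not support the claim that the total is a sum of days and events. The change is worth making before analysis, because it determines what is reported for a safety outcome.

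**What to change.** In the SAP:

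1. In Table 4B, count pain and infection as numbers of complications (episodes), and state the rule for when a new episode starts.
2. State that the heading row is the number of complications listed in that table, and never a sum that includes days.
3. Add a row for all access-related complications of grade 2 or higher, so that the section 5.1.2 outcome has an output in its defined unit. Table 4B alone leaves out grade 3 and above.
4. If treatment days are wanted, define them as a separate measure, report them as days per patient-year, and do not label the comparison an event rate ratio.

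The cost is some table wording and one derivation step. That step needs start and stop dates of treatment, or one record per complication. The SAP does not show how treatment days are captured. If only totals per patient were entered, episodes might have to be recovered from source records, so the sponsor should check this first.

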2.1. Trial design

It is a double-blind, multicenter randomized controlled trial with a superiority framework and a 1:1 individual participant treatment allocation ratio over two study arms. In the intervention group, only symptomatic vascular access stenosis detected by clinical monitoring are treated, whereas in the comparison group asymptomatic stenosis detected by surveillance are treated as well (current standard of care in the Netherlands). Prevalent hemodialysis patients with a functional arteriovenous vascular access are eligible to participate in the trial. Patients will be followed up for a minimum of 2 years and a maximum of 3 years (follow up will end for all participants when the last included patient has reached a 2 year follow-up period) and will be censored when their mode of renal replacement therapy is changed to kidney transplantation, peritoneal dialysis, or conservative treatment.

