2.4. Framework

Superiority framework. The intervention group will be compared to the control group. Analyses will be stratified for treatment center and for vascular access type (graft vs fistula). Every effort is made to establish eligibility of participants prior to randomization; no withdrawals due to ineligibility are allowed and the analyses include all participants enrolled. The primary analysis will be on the intention to treat population (i.e. no participants are withdrawn from analysis for lack of adherence to treatment allocation); exploratory on-treatment analyses will be performed. A comparison of included and excluded patients is done to provide insight into the external validity of the clinical trial. Every effort is made to avoid missing data, including assistance from dialysis nurses in obtaining patient-reported outcome measures during dialysis sessions. Primary outcome data are not expected to be missing, as interventions on vascular access will be reported in the patients' medical files. We expect no loss to follow-up in the study participants since they are observed three times per week in the dialysis unit. Patient-reported outcomes will be analysed using generalized estimating equations that allow for missing data. Other missing data will be handled by using 5 imputation cycles with regression methods. Outliers will not be removed from the analysis unless the data can clearly be shown to be erroneous.

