2.7. Timing of outcome assessments

Physical examination of the vascular access will be done at each dialysis session. Volume measurements by ultrasound dilution will be done every month. Duplex ultrasound examination of the vascular access will take place in case of flow dysfunction, and interventions for flow dysfunction are part of standard clinical care for hemodialysis patients. Subjects enrolled in the trial will be asked to fill out questionnaires (SF-VAQ, EQ-5D-5L, MCQ and PCQ) at baseline and every 3 months until 24 months of follow up.

3. Statistical Principles

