Problem on dialysis
Access care
Hospitalization
Worry about access longevity

Include only questionnaires with complete data. Questions are Likert scores from 1 to 7. Domain scores are the sum of the 4 questions. The total score is the sum of the 3 domains.

Sensitivity analysis: exclude patients with interventions on the current vascular access before enrollment

Statistical analysis: mixed linear model

Table 5C: Change in SF-VAQ scores with access-related interventions

	Before intervention (>30 days)	Around intervention (30 days before – 90 days after)	P	Clinically relevant change
Total score	Mean (SD)	Mean (SD)	...	%
Physical domain	Mean (SD)	Mean (SD)	...	%
Pain	Mean (SD)	Mean (SD)	...	
Bleeding	Mean (SD)	Mean (SD)	...	
Swelling	Mean (SD)	Mean (SD)	...	
Bruising	Mean (SD)	Mean (SD)	...	
Social functioning domain	Mean (SD)	Mean (SD)	...	%
Daily activities	Mean (SD)	Mean (SD)	...	
Appearance	Mean (SD)	Mean (SD)	...	
Sleep	Mean (SD)	Mean (SD)	...	
Bathing and showering	Mean (SD)	Mean (SD)	...	
Dialysis complications domain	Mean (SD)	Mean (SD)	...	%
Problem on dialysis	Mean (SD)	Mean (SD)	...	
Access care	Mean (SD)	Mean (SD)	...	
Hospitalization	Mean (SD)	Mean (SD)	...	
Worry about access longevity	Mean (SD)	Mean (SD)	...	

Compare SF-VAQ scores before (latest but >30 days before) and around (closest to the intervention but <30 days before and <90 days after) the access-related intervention. Calculate the proportion of patients with a clinically relevant change in SF-VAQ scores.

The clinically relevant change in SF-VAQ scores is defined as 0.5 times the standard deviation of the difference in SF-VAQ scores between two adjacent measurements in patients without vascular access-related interventions or vascular access-related (serious) adverse events.

Statistical analysis: paired Student t-test

Table 5D: Change in SF-VAQ scores with thrombosis

	Before thrombosis (>30 days)	After thrombosis (<90 days)	P	Clinically relevant change
Total score	Mean (SD)	Mean (SD)	...	%
Physical domain	Mean (SD)	Mean (SD)	...	%
Pain	Mean (SD)	Mean (SD)	...	
Bleeding	Mean (SD)	Mean (SD)	...	
Swelling	Mean (SD)	Mean (SD)	...	
Bruising	Mean (SD)	Mean (SD)	...	
Social functioning domain	Mean (SD)	Mean (SD)	...	%
Daily activities	Mean (SD)	Mean (SD)	...	
Appearance	Mean (SD)	Mean (SD)	...	
Sleep	Mean (SD)	Mean (SD)	...	
Bathing and showering	Mean (SD)	Mean (SD)	...	
Dialysis complications domain	Mean (SD)	Mean (SD)	...	%
Problem on dialysis	Mean (SD)	Mean (SD)	...	

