Access care	Mean (SD)	Mean (SD)	...	
Hospitalization	Mean (SD)	Mean (SD)	...	
Worry about access longevity	Mean (SD)	Mean (SD)	...	

Compare SF-VAQ scores before (latest but >30 days before) and after (earliest but <90 days after) the thrombosis. Calculate the proportion of patients with a clinically relevant change in SF-VAQ scores. The clinically relevant change in SF-VAQ scores is defined as 0.5 times the standard deviation of the difference in SF-VAQ scores between two adjacent measurements in patients without vascular access-related interventions or vascular access-related (serious) adverse events.

Statistical analysis: paired Student t-test

Table 5E: Predictors of SF-VAQ scores at baseline

	Total score		Physical domain		Social domain		Complications domain	
	β (95% CI)	P	β (95% CI)	P	β (95% CI)	P	β (95% CI)	P
Sex (male)								
Age (/year)								
Body mass index (/kg/m ²)								
Diabetes mellitus (yes)								
Dialysis treatments per week								
Vascular access type								
Arteriovenous fistula								
Radiocephalic fistula								
Brachiocephalic fistula								
Brachiobasilic fistula								
Arteriovenous graft								
Age vascular access (/month)								
Previous vascular access								
Previous vascular access interventions								
Baseline access flow (/100 mL/min)								

Groups are based on initial randomization. Include only questionnaires with complete data.

Statistical analysis: all variables will be entered into multivariable linear regression models

Check for assumptions of statistical model: linearity, multicollinearity, and independence of errors

Table 6A: Repeatability / Test-retest reliability of ultrasound dilution flow measurements

	Point estimate	95% CI
Standard error of measurements (SEM)		
Coefficient of variation (CV)		

Same observer under the same conditions using the same measurement instrument (test-retest)

Include all ultrasound dilution flow measurements with 3 replicates (N=...)

Check for assumptions of statistical model: normal distribution of measurements and homogeneity of variance within subjects

Table / Figure 6B: Reproducibility / Inter-session reliability of ultrasound dilution flow measurements

Without correction for blood pressure

	N	Bias	Limits of agreement
Flow measurements within 2 weeks			
All measurements		mL/min	mL/min
Only random controls		mL/min	mL/min
Flow measurements within 1 week			
All measurements		mL/min	mL/min
Only random controls		mL/min	mL/min

With correction for blood pressure

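### Table 5B classes each SF-VAQ score by the patient's total interventions over the whole follow-up, so scores are sorted by events that had not yet happened

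*SAP*

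**What the plan says.** All tables named here are in SAP section 6.

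- **Table 5B** is titled "Table 5B: SF-VAQ scores according to the number of interventions during follow-up". Its three columns are none, one, and more than one intervention during follow-up. The method line reads "Statistical analysis: mixed linear model". One sensitivity analysis drops patients whose current access had an intervention before enrolment. The table does not say which questionnaires enter or what terms the model has.
- **Schedule.** Section 2.7 has questionnaires completed "at baseline and every 3 months until 24 months of follow up". Section 2.1 states: "Patients will be followed up for a minimum of 2 years and a maximum of 3 years".
- **Table 5C** takes as its comparison score the one "around (closest to the intervention but <30 days before and <90 days after) the access-related intervention". Table 5D, its counterpart for thrombosis, uses the score "after (earliest but <90 days after) the thrombosis".
- **Between-group analysis.** Section 2.4, repeated in section 5.3, says: "Patient-reported outcomes will be analysed using generalized estimating equations that allow for missing data". Of Tables 5A to 5E, only 5A has monitoring and surveillance columns, and it covers baseline. No listed table reports EQ-5D-5L.

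**The concern.** A whole-follow-up count is known only when follow-up ends. Using it to class scores collected along the way conditions on the future, with two consequences.

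First, a score given while a patient had had no intervention is averaged into the one or more-than-one column if an intervention came later. If questionnaires stop at month 24 and follow-up continues to month 36, a patient whose only intervention falls in month 30 contributes nothing but pre-intervention scores to the one-intervention column.

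Second, the count depends on time at risk. Section 2.3 expects 20% of participants to leave per year. Those who leave early have had less opportunity for an intervention and so collect in the zero column, whatever their access would have done later. Column membership therefore partly reflects length of follow-up, and the reasons for leaving (transplantation, death, withdrawal) may themselves relate to the scores.

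At stake is the trial's description of how interventions relate to patients' satisfaction with their access. The randomised primary comparison is not affected.

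**Working it through.** The SAP gives no figure to reproduce here. The calculations below show how far a whole-follow-up count can differ from the count at the questionnaire date.

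**Inputs from the SAP.** Nine questionnaires at months q = 0, 3, ..., 24 (section 2.7); follow-up F of 24 to 36 months (section 2.1); 1.77 interventions per patient-year and a target reduction of 0.25 (section 2.3).

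**Assumptions not in the SAP.** Intervention times are uniform over follow-up, and questionnaires are complete and on schedule. Where a rate is needed, it is the midpoint of 1.77 and 1.77 − 0.25 = 1.52, that is 1.645 per year, the same for all patients.

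**1. One-intervention column.** The chance that a score at month q precedes the intervention is 1 − q/F. The mean q is 12 months over all nine questionnaires and 13.5 months without baseline.

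| Follow-up F | Share before, all scores: 1 − 12/F | Without baseline: 1 − 13.5/F | Intervention after month 24: 1 − 24/F |
|---|---|---|---|
| 24 months | 50% | 44% | 0% |
| 30 months | 60% | 55% | 20% |
| 36 months | 67% | 63% | 33% |

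A simulation of 400,000 intervention times gave the same values.

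**2. More-than-one column, F = 24 months.** The expected count is 1.645 × 2 = 3.29.

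- Column sizes: zero, e^−3.29 = 4%; one, 3.29 × e^−3.29 = 12%; more than one, the remaining 84%.
- Let m = 1.645q/12 and k = 3.29 − m. A score at month q precedes the first intervention with probability e^−m × [1 − e^−k(1 + k)] / 0.840. Averaged over the nine questionnaires this is 26.5%.
- Scores before the second intervention also carry the wrong label. Adding m·e^−m × (1 − e^−k) / 0.840 and averaging gives 47%.

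**3. Dependence on length of follow-up.** The chance of landing in the zero column is e^(−1.645 × 0.5) = 44% with 6 months of follow-up and e^(−1.645 × 2) = 4% with 24 months. If rates vary between patients (gamma frailty, assumed variance 1), the chances are 1/(1 + 0.8225) = 55% and 1/(1 + 3.29) = 23%. The contrast narrows but remains.

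**4. Table 5C window.** Questionnaires are about 91.3 days apart. A score less than 30 days before the intervention is always closer than the next one, which falls more than 61 days after, so it is always selected. That happens in 30/91.3 = 33% of cases. Simulation that also requires an earlier score for comparison gives 30% with 24 months of follow-up and 33% with 36 months.

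**The case against.** **Table 5B may be incomplete rather than wrong.** It does not state which questionnaires or model terms are used, so the analyst might intend a time-updated count. That is possible, but the column headings describe the whole follow-up and no other rule is given. The sensitivity analysis deals with interventions before enrolment and leaves this problem untouched.

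**The percentages depend on their assumptions.** This stands.

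- The rate of 1.645 is not in the SAP. It is derived from figures for a retrospective cohort, while the trial excludes recent thrombosis, low flow and planned interventions. Section 2.3 also gives different rates for fistulas (1.56) and grafts (3.30).
- At that rate the one-intervention column holds only about 12% of patients at 24 months, so a reader should not infer that half of all scores precede any intervention. In the larger column the share before the first intervention is 26.5%.
- The 67% needs questionnaires to stop at month 24. Section 5.1.2 has them every 3 months throughout follow-up, and on that reading the share stays near 50%.

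**Table 5C is openly labelled.** A reader might infer that it wrongly credits earlier scores to the intervention. The document does not support that: the column is headed as a window around the intervention, from 30 days before to 90 days after. Capturing the episode of dysfunction that led to treatment is a defensible aim. What remains is that the selected scores mix before and after, and that Tables 5C and 5D are not comparable.

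**A between-group analysis of patient-reported outcomes is intended.** A reader might infer from Tables 5A to 5E that none is planned. Section 2.4 sets a framework comparing the groups and, in the same section, names GEE for these outcomes. What is missing is mainly detail: the contrast, the time points and a table. A simple comparison of arms would also overlook that patients are randomised again after interventions and can change group (Figure 2E, Table 2L).

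**Conclusion.** The point holds for Table 5B. Followed as written, it classifies patients by future events and lets length of follow-up influence the columns. This follows from the definition and needs none of the calculated figures. Under uniform timing and complete questionnaires to month 24, about half the scores of a patient with exactly one intervention precede it with 24 months of follow-up. That figure is illustrative. The net direction of the bias cannot be fixed from the document, because earlier scores may already reflect dysfunction and early leavers may differ in either direction.

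The window in Table 5C and the absence of a post-baseline table by group are secondary: the first is a labelled choice that would benefit from a companion row, the second a gap in detail.

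**What to change.** 1. **Table 5B.** Define the columns by the number of interventions up to each questionnaire date (0, 1, more than 1). Enter this as a time-varying term in the mixed model, adjusted for time since randomisation and baseline score. With the baseline score as a covariate, only later questionnaires are outcomes. The result remains a non-randomised association and should be labelled so.
2. **Table 5C.** Keep the present window and add a sensitivity row using only scores within 90 days after the intervention, matching Table 5D.
3. **GEE analysis.** If a table of post-baseline SF-VAQ and EQ-5D-5L by study group is added, state whether group means initial or current allocation, and to which group a score given after a change of allocation belongs.

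The cost is SAP wording, one extra row and possibly one extra table. Intervention and questionnaire dates are already needed for Table 5C, so no new data are required. The change should be made before the scores are analysed by group or by intervention.
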